8.7.3 Physical Examination

Physical examinations will include assessments of general appearance; head, eyes, ears, nose, and throat; the cardiovascular, dermatologic, lymphatic, respiratory, gastrointestinal,

genitourinary, musculoskeletal, and neurologic systems. Physical examination abnormality findings will be listed over time by subject.

8.7.4 Electrocardiogram

The following ECG results and change from baseline results will be summarized and provided in subject listing:

- RR Duration (msec)
- Heart Rate (beats/min)
- PR Duration (msec)
- QRS Duration (msec)
- QT Duration (msec)
- QTcB - Bazett's Correction Formula (msec)
- QTcF - Fridericia's Correction Formula (msec)
- Overall Statement (Categorical indicator of evaluability, abnormality and clinical significance of abnormality)

8.7.5 Select Clinical Laboratory Parameters

Clinical laboratory data will be summarized by the type of laboratory test. Reference ranges and markedly abnormal results will be used in the summary of laboratory data.

Summary statistics will be calculated for each laboratory analyte at baseline and at each scheduled time point. Changes from baseline results will be presented in pre- versus post-treatment cross tabulations (with classes for below, within, and above normal ranges). A listing of subjects with any markedly abnormal laboratory results will be provided. The frequency and percentage of subjects who experience abnormal clinical laboratory results (i.e., outside of reference ranges) and/or clinically significant abnormalities will be presented for each clinical laboratory measurement.

The following laboratory results will be summarized by time point for the observed value as well as for the change from baseline value:

- Chemistry: Alanine aminotransferase (ALT), Alkaline phosphatase, Aspartate aminotransferase (AST), Bilirubin (total), Blood urea nitrogen (BUN), Calcium, Chloride, Serum creatinine, Gamma-glutamyl transpeptidase (GGT), Serum glucose, Potassium, Protein (albumin and total), Sodium
- Hematology: Hematocrit, Hemoglobin, Platelet count, Red blood cell (RBC) count, White blood cell (WBC) count, Beta-hydroxybutyrate (BHB) (at Screening)
- Urinalysis: Appearance, Color, pH, Specific gravity, Ketones, Protein, Glucose, Pregnancy test (if applicable)

For fasting serum glucose, triglycerides, ALT, AST and GGT, CTCAE severity grades will be summarized in shift tables pairing each subject's baseline severity grade with the subject's highest post-baseline severity grade.

Specifically, CTCAE severity grades for increased triglycerides are:

- Grade 1: 150 – 300 mg/dL; 1.71 – 3.42 mmol/L
- Grade 2: > 300 – 500 mg/dL; > 3.42 – 5.7 mmol/L
- Grade 3: >500 – 1000 mg/dL; > 5.7 – 11.4 mmol/L
- Grade 4: >1000 mg/dL; > 11.4 mmol/L

CTCAE severity grades for hypoglycemia are:

- Grade 1: <LLN – 55 mg/dL; <LLN – 3.0 mmol/L
- Grade 2: <55 – 40 mg/dL; <3.0 – 2.2 mmol/L
- Grade 3: <40 – 30 mg/dL; <2.2 – 1.7 mmol/L
- Grade 4: < 30 mg/dL; <1.7 mmol/L

CTCAE severity grades for increased ALT and increased AST are:

- Grade 1: >ULN to 3.0 x ULN
- Grade 2: >3.0 x ULN to 5.0 x ULN
- Grade 3: >5.0 x ULN to 20.0 x ULN
- Grade 4: >20.0 x ULN

And CTCAE severity grades for increased GGT are:

- Grade 1: >ULN to 2.5 x ULN
- Grade 2: >2.5 x ULN to 5.0 x ULN
- Grade 3: >5.0 x ULN to 20.0 x ULN
- Grade 4: >20.0 x ULN

Hy's Law criteria will be applied against test results. Subjects with serum total bilirubin >2 x ULN and ALT or AST >3 x ULN will be considered positive for Hy's law status. Results will be presented in shift tables. For Hy's Law, shift tables will be produced:

- Hy's Law negative at baseline, remaining Hy's Law negative throughout the study
- Hy's Law negative at baseline, becoming Hy's Law positive at any point during the study

- Hy's Law positive at baseline and Hy's Law negative throughout the study
- Hy's Law positive at baseline and Hy's Law positive at any point during the study

A data listing of all subjects who are Hy's Law positive will be produced.

8.7.6 Suicidal Ideation and Behavior

Assessment of suicidal ideation and behavior is a regular part of development programs involving AEDs and other neurologic drugs with central nervous system activity ([FDA Draft Guidance 2012](#)). The Columbia Suicide Severity Rating Scale (C-SSRS) is a standardized suicidal rating instrument used to assess the suicidal ideation and behavior in an at-risk pediatric population ([Posner et al. 2011](#)).

The following outcomes are C-SSRS categories and have binary responses (yes/no). The categories have been re-ordered from the actual scale to facilitate the definitions of the composite and comparative endpoints, and to enable clarity in the presentation of the results.

- Category 1 – Wish to be Dead
- Category 2 – Non-specific Active Suicidal Thoughts
- Category 3 – Active Suicidal Ideation with Any Methods (Not Plan) without Intent to Act
- Category 4 – Active Suicidal Ideation with Some Intent to Act, without Specific Plan
- Category 5 – Active Suicidal Ideation with Specific Plan and Intent
- Category 6 – Preparatory Acts or Behavior
- Category 7 – Aborted Attempt
- Category 8 – Interrupted Attempt
- Category 9 – Actual Attempt (non-fatal)
- Category 10 – Completed Suicide

Self-injurious behavior without suicidal intent is also a C-SSRS outcome (although not suicide-related) and has a binary response (yes/no).

Composite endpoints based on the above categories are defined below.

- Suicidal ideation: A “yes” answer at any time during treatment to any one of the five suicidal ideation questions (Categories 1-5) on the C-SSRS
- Suicidal behavior: A “yes” answer at any time during treatment to any one of the five suicidal behavior questions (Categories 6-10) on the C-SSRS
- Suicidal ideation or behavior: A “yes” answer at any time during treatment to any one of the ten suicidal ideation and behavior questions (Categories 1-10) on the C-SSRS

C-SSRS endpoints will be summarized by treatment group and presented in a listing.

8.7.7 Prior and Concomitant Medications

A *prior medication* is defined as any medication started before the date of the first dose of study drug. A *concomitant medication* is defined as any medication taken on or after the date of the first dose of study drug. A medication started before the date of the first dose of study drug and also taken after the date of first dose of study drug will be counted both as a prior and concomitant medication.

Both prior and concomitant medications will be coded by drug name and therapeutic class using WHO Drug Dictionary Enhanced Version 2014 December or newer and summarized by treatment group for the Safety Analysis Set and listed by subject. If a subject took a specific medication multiple times or took multiple medications within a specific therapeutic class, that subject would be counted only once for the coded drug name or therapeutic class.

8.7.8 Pharmacokinetics of UX007

Summary statistics, including mean, standard deviation, coefficient of variation, geometric mean, median, minimum, and maximum will be presented over time for plasma peak levels of UX007, plasma levels of UX007 metabolites [C4 ketone (BHB), C5 ketones (beta-hydroxypentanoate [BHP]), and heptanoate], non-fasting BHB and trough (pre-dose [within 15 minutes]) UX007 at each available time point. Data will be listed for all subjects with available data. All subjects and samples excluded from the analysis will be clearly documented in the study report.

9 PLANNED DATA PRESENTATIONS

Data presentations planned to support writing the UX007G-CL201 CSR are listed in [Table 6](#).

Table 6: Planned Data Presentations

Output Type	Title
	Demographic Data
Table	Subject Disposition – Randomized Population
Table	Protocol Deviations – Efficacy Analysis Set
Table	Demographics – Efficacy Analysis Set
Table	Demographics by Age Group – Efficacy Analysis Set
Table	Glut1 DS Disease History – Efficacy Analysis Set
Table	Seizure History – Efficacy Analysis Set
Table	Study Drug Exposure – Efficacy Analysis Set
Table	Summary of Diet Diary Review – Efficacy Analysis Set
Table	Dosing Compliance – Days Dose Missed by Study Period – Efficacy Analysis Set
	Primary and Secondary Efficacy Analyses – Seizures
Table	Seizures – Week 8 Analysis – Summary – Efficacy Analysis Set
Table	Observable Seizures – Week 8 Analysis – Summary – Efficacy Analysis Set
Table	Absence Seizures – Week 8 Analysis – Summary – Efficacy Analysis Set
Table	Seizures – Reduction from Baseline – Week 8 Analysis – ANCOVA – Efficacy Analysis Set
Table	Observable Seizures – Reduction from Baseline – Week 8 Analysis – ANCOVA – Efficacy Analysis Set
Table	Absence Seizures – Reduction from Baseline – Week 8 Analysis – ANCOVA – Efficacy Analysis Set
Table	Seizure Response – Week 8 Analysis – Logistic Regression – Efficacy Analysis Set
Table	Observable Seizure Response – Week 8 Analysis – Logistic Regression – Efficacy Analysis Set
Table	Absence Seizure Response – Week 8 Analysis – Logistic Regression – Efficacy Analysis Set
	Additional Efficacy Analyses – Seizures
Table	Seizures – Week 8 Analysis – Summary – Per Protocol Analysis Set
Table	Observable Seizures – Week 8 Analysis – Summary – Per Protocol Analysis Set
Table	Absence Seizures – Week 8 Analysis – Summary – Per Protocol Analysis Set
Table	Seizures – Reduction from Baseline – Week 8 Analysis – ANCOVA – Per Protocol Analysis Set
Table	Observable Seizures – Reduction from Baseline – Week 8 Analysis – ANCOVA – Per Protocol Analysis Set
Table	Absence Seizures – Reduction from Baseline – Week 8 Analysis – ANCOVA – Per Protocol Analysis Set
Table	Seizure Response – Week 8 Analysis – Logistic Regression – Per Protocol Analysis Set
Table	Observable Seizure Response – Week 8 Analysis – Logistic Regression – Per Protocol Analysis Set
Table	Absence Seizure Response – Week 8 Analysis – Logistic Regression – Per Protocol Analysis Set

Output Type	Title
Table	Absence Seizures – Week 8 Analysis – Summary – Efficacy Analysis Set – Absence at Baseline
Table	Absence Seizures – Reduction from Baseline – Week 8 Analysis – ANCOVA – Efficacy Analysis Set – Absence at Baseline
Table	Absence Seizure Response – Week 8 Analysis – Logistic Regression – Efficacy Analysis Set – Absence at Baseline
Table	Seizures – Week 8 Analysis – Summary – Efficacy Analysis Set – Dosing Compliance $\geq 80\%$
Table	Observable Seizures – Week 8 Analysis – Summary – Efficacy Analysis Set – Dosing Compliance $\geq 80\%$
Table	Absence Seizures – Week 8 Analysis – Summary – Efficacy Analysis Set – Dosing Compliance $\geq 80\%$
Table	Seizures – Reduction from Baseline – Week 8 Analysis – ANCOVA – Efficacy Analysis Set – Dosing Compliance $\geq 80\%$
Table	Observable Seizures – Reduction from Baseline – Week 8 Analysis – ANCOVA – Efficacy Analysis Set – Dosing Compliance $\geq 80\%$
Table	Absence Seizures – Reduction from Baseline – Week 8 Analysis – ANCOVA – Efficacy Analysis Set – Dosing Compliance $\geq 80\%$
Table	Seizure Response – Week 8 Analysis – Logistic Regression – Efficacy Analysis Set – Dosing Compliance $\geq 80\%$
Table	Observable Seizure Response – Week 8 Analysis – Logistic Regression – Efficacy Analysis Set – Dosing Compliance $\geq 80\%$
Table	Absence Seizure Response – Week 8 Analysis – Logistic Regression – Efficacy Analysis Set – Dosing Compliance $\geq 80\%$
Table	Seizures – Reduction from Baseline – Week 8 Analysis – ANCOVA – Efficacy Analysis Set – Alternate Imputation Method
Table	Observable Seizures – Reduction from Baseline – Week 8 Analysis – ANCOVA – Efficacy Analysis Set – Alternate Imputation Method
Table	Absence Seizures – Reduction from Baseline – Week 8 Analysis – ANCOVA – Efficacy Analysis Set – Alternate Imputation Method
Table	Seizure Response – Week 8 Analysis – Logistic Regression – Efficacy Analysis Set – Alternate Imputation Method
Table	Observable Seizure Response – Week 8 Analysis – Logistic Regression – Efficacy Analysis Set – Alternate Imputation Method
Table	Absence Seizure Response – Week 8 Analysis – Logistic Regression – Efficacy Analysis Set – Alternate Imputation Method
Table	Seizures – Reduction from Baseline – Week 8 Analysis – ANCOVA – Efficacy Analysis Set – Complete Case Method
Table	Observable Seizures – Reduction from Baseline – Week 8 Analysis – ANCOVA – Efficacy Analysis Set – Complete Case Method
Table	Absence Seizures – Reduction from Baseline – Week 8 Analysis – ANCOVA – Efficacy Analysis Set – Complete Case Method
Table	Seizure Response – Week 8 Analysis – Logistic Regression – Efficacy Analysis Set – Complete Case Method
Table	Observable Seizure Response – Week 8 Analysis – Logistic Regression – Efficacy Analysis Set – Complete Case Method

Output Type	Title
Table	Absence Seizure Response – Week 8 Analysis – Logistic Regression – Efficacy Analysis Set – Complete Case Method
Table	Seizures – Week 8 Analysis – Summary – Efficacy Analysis Set – Alternate Seizure Frequency Derivation
Table	Seizures – Reduction from Baseline – Week 8 Analysis – ANCOVA – Efficacy Analysis Set – Alternate Seizure Frequency Derivation
Table	Seizure Response – Week 8 Analysis – Logistic Regression – Efficacy Analysis Set – Alternate Seizure Frequency Derivation
Table	Seizures – Week 8 Analysis – Summary – Efficacy Analysis Set – Analysis Including Dose Titration Period
Table	Observable Seizures – Week 8 Analysis – Summary – Efficacy Analysis Set – Analysis Including Dose Titration Period
Table	Seizures – Reduction from Baseline – Week 8 Analysis – ANCOVA – Efficacy Analysis Set – Analysis Including Dose Titration Period
Table	Observable Seizures – Reduction from Baseline – Week 8 Analysis – ANCOVA – Efficacy Analysis Set – Analysis Including Dose Titration Period
Table	Seizure Response – Week 8 Analysis – Logistic Regression – Efficacy Analysis Set – Analysis Including Dose Titration Period
Table	Observable Seizure Response – Week 8 Analysis – Logistic Regression – Efficacy Analysis Set – Analysis Including Dose Titration Period
	Secondary Efficacy Analyses
Table	CANTAB Simple Choice Median Reaction Time – Week 8 Analysis – Summary – Efficacy Analysis Set – CANTAB
Table	CANTAB Five Choice Median Reaction Time – Week 8 Analysis – Summary – Efficacy Analysis Set – CANTAB
Table	CANTAB Simple Choice Standard Deviation – Week 8 Analysis – Summary – Efficacy Analysis Set – CANTAB
Table	CANTAB Spatial Span Length – Week 8 Analysis – Summary – Efficacy Analysis Set – CANTAB
Table	CANTAB Paired Associates Learning Test Total Errors (Adjusted) – Week 8 Analysis – Summary – Efficacy Analysis Set – CANTAB
Table	CANTAB Paired Associates Learning Test First Trial Memory Score – Week 8 Analysis – Summary – Efficacy Analysis Set – CANTAB
Table	CANTAB Spatial Working Memory Between Errors – Week 8 Analysis – Summary – Efficacy Analysis Set – CANTAB
Table	CANTAB Spatial Working Memory Strategy – Week 8 Analysis – Summary – Efficacy Analysis Set – CANTAB
Table	CANTAB – Change from Baseline – Week 8 Analysis – GEE – Efficacy Analysis Set – CANTAB
Table	CANTAB – Change from Baseline – Week 8 Analysis – GEE – Per Protocol Analysis Set – CANTAB
Table	6MWT Distance (meters) – Week 8 Analysis – Summary – Efficacy Analysis Set – 6MWT
Table	6MWT Distance (percent predicted) – Week 8 Analysis – Summary – Efficacy Analysis Set – 6MWT
Table	Onset of PED – Week 8 Analysis – Summary – Efficacy Analysis Set – 6MWT

Output Type	Title
Table	6MWT – Change from Baseline – Week 8 Analysis – GEE – Efficacy Analysis Set – 6MWT
Table	Onset of PED – Week 8 Analysis – GEE – Efficacy Analysis Set – 6MWT
Table	GMFM-88 Total Score – Week 8 Analysis – Summary – Efficacy Analysis Set – GMFM-88
Table	GMFM-88 Total Score – Change from Baseline – Week 8 Analysis – GEE – Efficacy Analysis Set – GMFM-88
	Exploratory Efficacy Analyses
Table	Frequency of Seizure Types via Diary – Week 8 Analysis – Summary – Efficacy Analysis Set
Table	Frequency of Seizure Types via EEG – Week 8 Analysis – Summary – Efficacy Analysis Set
Table	CGI-S and CGI-I – Week 8 Analysis – Summary – Efficacy Analysis Set – CGI-I
Table	CGI-I – Week 8 Analysis – t-tests – Efficacy Analysis Set
Table	SF-10 – Week 8 Analysis – Summary – Efficacy Analysis Set – SF-10
Table	SF-12 v2 – Week 8 Analysis – Summary – Efficacy Analysis Set – SF-12
Table	SF-10 – Change from Baseline – Week 8 Analysis – t-tests – Efficacy Analysis Set
Table	SF-12 – Change from Baseline – Week 8 Analysis – t-tests – Efficacy Analysis Set
Table	CNS – Week 8 Analysis – Summary – Efficacy Analysis Set – CNS
Table	CNS – Change from Baseline – Week 8 Analysis – t-tests – Efficacy Analysis Set
	Safety Analyses of Adverse Events
Table	Overall Summary of Adverse Events – Safety Analysis Set
Table	Overall Summary of Adverse Events by Study Period – Safety Analysis Set
Table	Treatment Emergent Adverse Events by System Organ Class and Preferred Term – Safety Analysis Set
Table	Serious Treatment Emergent Adverse Events by System Organ Class and Preferred Term – Safety Analysis Set
Table	Treatment Emergent Adverse Events by System Organ Class, Preferred Term and Greatest Severity – Safety Analysis Set
Table	Treatment Emergent Adverse Events by System Organ Class, Preferred Term and Greatest Reported Relationship – Safety Analysis Set
Table	Grade 3 or 4 Treatment Emergent Adverse Events by System Organ Class and Preferred Term – Safety Analysis Set
Table	Related Treatment Emergent Adverse Events by System Organ Class and Preferred Term – Safety Analysis Set
Table	Gastrointestinal Treatment Emergent Adverse Events by Preferred Term – Safety Analysis Set
Table	UX007 Emergent Adverse Events by System Organ Class and Preferred Term – Safety Analysis Set
Table	Serious UX007 Emergent Adverse Events by System Organ Class and Preferred Term – Safety Analysis Set
Table	Related Serious Treatment Emergent Adverse Events by System Organ Class and Preferred Term – Safety Analysis Set
Table	Related Gastrointestinal Treatment Emergent Adverse Events by Preferred Term – Safety Analysis Set
Table	Treatment Emergent Adverse Events by System Organ Class and Preferred Term (by age group) – Safety Analysis Set

Output Type	Title
Table	Treatment Emergent Adverse Events by System Organ Class and Preferred Term (by gender) – Safety Analysis Set
Table	Treatment Emergent Adverse Events by System Organ Class and Preferred Term (by seizure type) – Safety Analysis Set
Table	Treatment Emergent Adverse Events by Preferred Term – Safety Analysis Set
Table	Serious Treatment Emergent Adverse Events by Preferred Term – Safety Analysis Set
Table	Related Treatment Emergent Adverse Events by Preferred Term – Safety Analysis Set
Table	Exposure Adjusted Treatment Emergent Adverse Event Incidence by System Organ Class and Preferred Term – Safety Analysis Set
Table	Exposure Adjusted UX007 Emergent Adverse Event Incidence by System Organ Class and Preferred Term – Safety Analysis Set
	Safety Analyses of Laboratory and Other Parameters
Table	Chemistry Laboratory Data Summary – Safety Analysis Set
Table	Chemistry Laboratory Shift Table – Safety Analysis Set
Table	Hematology Laboratory Data Summary – Safety Analysis Set
Table	Hematology Laboratory Shift Table – Safety Analysis Set
Table	Urinalysis Laboratory Data Summary – Safety Analysis Set
Table	Urinalysis Laboratory Shift Table – Safety Analysis Set
Table	Chemistry Abnormal and/or Clinically Significant Findings – Safety Analysis Set
Table	Hematology Abnormal and/or Clinically Significant Findings – Safety Analysis Set
Table	Urinalysis Abnormal and/or Clinically Significant Findings – Safety Analysis Set
Table	Vital Signs and Weight Summary – Safety Analysis Set
Table	ECG Results Summary – Safety Analysis Set
Table	ECG Results Shift Table – Safety Analysis Set
Table	Hy’s Law Status Shift Table – Safety Analysis Set
Table	PK Parameters Summary – Safety Analysis Set
Table	Suicidal Ideation Summary – Safety Analysis Set
	Efficacy Analyses Figures
Figure	Seizures – Week 8 Analysis – Individual and Geometric Mean with 90% CI – Efficacy Analysis Set
Figure	Observable Seizures – Week 8 Analysis – Individual and Geometric Mean with 90% CI – Efficacy Analysis Set – Observable Seizures
Figure	Observable Seizures – Week 8 Analysis – Individual and Geometric Mean with 90% CI – Efficacy Analysis Set – Observable Seizures Only
Figure	Absence Seizures – Week 8 Analysis – Individual and Geometric Mean with 90% CI – Efficacy Analysis Set – Absence Seizures
Figure	Absence Seizures – Week 8 Analysis – Individual and Geometric Mean with 90% CI – Efficacy Analysis Set – Absence Seizures Only
Figure	Seizures – Week 8 Analysis – Percent Reduction from Baseline to Week 8 – Cumulative Distribution Function – Efficacy Analysis Set
Figure	Observable Seizures – Week 8 Analysis – Percent Reduction from Baseline to Week 8 – Cumulative Distribution Function – Efficacy Analysis Set – Observable Seizures

Output Type	Title
Figure	Observable Seizures – Week 8 Analysis – Percent Reduction from Baseline to Week 8 – Cumulative Distribution Function – Efficacy Analysis Set – Observable Seizures Only
Figure	Absence Seizures – Week 8 Analysis – Percent Reduction from Baseline to Week 8 – Cumulative Distribution Function – Efficacy Analysis Set – Absence Seizures
Figure	Absence Seizures – Week 8 Analysis – Percent Reduction from Baseline to Week 8 – Cumulative Distribution Function – Efficacy Analysis Set – Absence Seizures Only
Figure	Seizures – Week 8 Analysis – Percent Reduction from Baseline to Week 8 with 90% CI – Efficacy Analysis Set
Figure	Seizure Response – Week 8 Analysis – Efficacy Analysis Set
Figure	Observable Seizures – Week 8 Analysis – Percent Reduction from Baseline to Week 8 with 90% CI – Efficacy Analysis Set
Figure	Observable Seizure Response – Week 8 Analysis – Efficacy Analysis Set
Figure	Absence Seizures – Week 8 Analysis – Percent Reduction from Baseline to Week 8 with 90% CI – Efficacy Analysis Set
Figure	Absence Seizure Response – Week 8 Analysis – Efficacy Analysis Set
Figure	CANTAB Simple Choice Median Reaction Time – Week 8 Analysis – Individual and Mean with 90% CI – Efficacy Analysis Set
Figure	CANTAB Five Choice Median Reaction Time – Week 8 Analysis – Individual and Mean with 90% CI – Efficacy Analysis Set
Figure	CANTAB Simple Choice Standard Deviation – Week 8 Analysis – Individual and Mean with 90% CI – Efficacy Analysis Set
Figure	CANTAB Spatial Span Length – Week 8 Analysis – Individual and Mean with 90% CI – Efficacy Analysis Set
Figure	CANTAB Paired Associates Learning Test Total Errors (Adjusted) – Week 8 Analysis – Individual and Mean with 90% CI – Efficacy Analysis Set
Figure	CANTAB Paired Associates Learning Test First Trial Memory Score – Week 8 Analysis – Individual and Mean with 90% CI – Efficacy Analysis Set
Figure	CANTAB Spatial Working Memory Between Errors – Week 8 Analysis – Individual and Mean with 90% CI – Efficacy Analysis Set
Figure	CANTAB Spatial Working Memory Strategy – Week 8 Analysis – Individual and Mean with 90% CI – Efficacy Analysis Set
Figure	6MWT Distance (meters) – Week 8 Analysis – Individual and Mean with 90% CI – Efficacy Analysis Set
Figure	6MWT Distance (percent predicted) – Week 8 Analysis – Individual and Mean with 90% CI – Efficacy Analysis Set
Figure	GMFM-88 Total Score – Week 8 Analysis – Individual and Mean with 90% CI – Efficacy Analysis Set
Figure	SF-10 – Week 8 Analysis – Efficacy Analysis Set
Figure	SF-12 – Week 8 Analysis – Efficacy Analysis Set
Figure	CGI-I – Week 8 Analysis – Efficacy Analysis Set
	Demographics Listings
Listing	Subject Disposition – Randomized Population
Listing	Analysis Sets – Randomized Population

Output Type	Title
Listing	Subjects Who Failed to Meet One or More Inclusion/Exclusion Criteria – Screened Population
Listing	Protocol Deviations – Screened Population
Listing	Demographics and Baseline Characteristics – Randomized Population
Listing	Glut1 DS Disease Diagnosis and History – Screened Population
Listing	Ketogenic Diet History – Screened Population
Listing	Seizure History – Screened Population
Listing	Medical History – Screened Population
Listing	Prior and Concomitant Medications – Screened Population
Listing	Study Drug Dosing – Randomized Population
Listing	Dosing Compliance and Missed Doses – Randomized Population
	Efficacy Listings
Listing	Seizures – Randomized Population
Listing	Seizure Classification by Diary – Seizure Frequency by Type – Randomized Population
Listing	Seizure Classification by EEG – Seizure Frequency by Type – Randomized Population
Listing	CANTAB – Randomized Population
Listing	6MWT – Randomized Population
Listing	GMFM-88 Scores – Randomized Population
Listing	CGI-I – Randomized Population
Listing	SF-10 – Randomized Population
Listing	SF-12 v2 Questions – Randomized Population
Listing	SF-12 v2 Domain and Component Scores – Randomized Population
Listing	CNS – Randomized Population
Listing	PPVT – Randomized Population
Listing	PEDI-CAT – Randomized Population
Listing	Beery-VMI and Raven’s Coloured Progressive Matrices – Randomized Population
Listing	Gait Analysis – Randomized Population
	Safety Listings
Listing	Treatment Emergent Adverse Events – Safety Analysis Set
Listing	Serious Treatment Emergent Adverse Events – Safety Analysis Set
Listing	UX007 Emergent Adverse Events – Safety Analysis Set
Listing	Serious UX007 Emergent Adverse Events – Safety Analysis Set
Listing	Adverse Events During the Run-In Period – Safety Analysis Set
Listing	Adverse Events Leading to Withdrawal from Study or Discontinuation from Study Drug – Safety Analysis Set
Listing	Treatment Emergent Adverse Events Leading to Death – Safety Analysis Set
Listing	Chemistry Laboratory Data – Safety Analysis Set
Listing	Hematology Laboratory Data – Safety Analysis Set
Listing	Urinalysis Laboratory Data – Safety Analysis Set

Output Type	Title
Listing	PK Data – Safety Analysis Set
Listing	Suicidal Ideation – Safety Analysis Set
Listing	Vital Signs and Weight – Safety Analysis Set
Listing	ECG – Safety Analysis Set
Listing	Laboratory Results and Hy's Law – Safety Analysis Set

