8.6.1 Comparisons Between UX007 and Placebo Groups

Comparisons of primary and secondary endpoints will be performed to test for a difference in the endpoint between UX007 and placebo groups during the double-blind placebo-controlled treatment period. Model based estimates will be presented, with 90% confidence intervals, for each endpoint by treatment group and also for the treatment effect (difference between treatment groups for continuous endpoints and difference between treatment groups for binary endpoints).

Endpoints measured during the double-blind placebo-controlled treatment period only at Week 8 and those measured at both Week 4 and Week 8 will be analyzed differently as described below. Endpoints measured only at Week 8 include those derived from the seizure diary and EEG. Endpoints measured at both Week 4 and Week 8 included those derived from CANTAB, 6MWT and GMFM-88.

Continuous Endpoints:

- Continuous endpoints measured only at Week 8 will be analyzed using linear regression (ANCOVA), with change from baseline to Week 8 as the response variable, treatment group (UX007 vs. placebo) as the primary variable of interest and an appropriate baseline value as an additional covariate.
- Continuous endpoints measured at both Week 4 and Week 8 will be analyzed using generalized estimating equations (GEE), with change from baseline at each timepoint as the response variable; treatment group (UX007 vs. placebo), a factor for visit, visit by treatment interaction and an appropriate baseline value as covariates; identity link function and exchangeable within subject working correlation matrix. The comparison of interest will be based on the LS means difference at Week 8.

Binary Endpoints:

- Categorical (binary) endpoints measured only at Week 8 will be analyzed using logistic regression, with a yes/no indicator as the response variable, treatment group (UX007 vs. placebo) as the primary variable of interest and an appropriate baseline value as an additional covariate.

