8.6.5 Exploratory Efficacy Endpoints

Summary statistics, including p-values for differences between treatment groups during the double-blind placebo-controlled treatment period, will be provided by visit for the following exploratory endpoints over the entire study period by treatment group and overall: specific seizure types derived from seizure diary, specific seizure types derived from EEG, CNS, CGI-I, SF-10 and SF-12 v2.

A data listing will be provided for the following exploratory endpoints available at select sites over the entire study period: PPVT, PEDI-CAT, Gait analysis during 6-minute walk test (6MWT), GMFM-88 domains (lying/rolling, sitting, crawling/kneeling, standing, and walking/running/jumping), Beery-VMI and RCPM.

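### Exploratory Week 8 t-tests on change in CNS, SF-10 and SF-12 omit the baseline covariate that the SAP already uses for endpoints of the same structure

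*SAP*

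**What the plan says.** SAP Section 8.6.5 covers CNS, CGI-I, SF-10 and SF-12 and plans "Summary statistics, including p-values for differences between treatment groups during the double-blind placebo-controlled treatment period, will be provided by visit". It does not say which test produces them. Table 5 and Appendix A list only summary statistics for these endpoints.

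The test appears only in the output titles of Table 6 (SAP Section 9): "CNS – Change from Baseline – Week 8 Analysis – t-tests – Efficacy Analysis Set", "SF-10 – Change from Baseline – Week 8 Analysis – t-tests – Efficacy Analysis Set" and "SF-12 – Change from Baseline – Week 8 Analysis – t-tests – Efficacy Analysis Set". No part of either document adds a baseline covariate to these tests.

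Section 8.6.1 is limited to the higher tiers: "Comparisons of primary and secondary endpoints will be performed to test for a difference in the endpoint between UX007 and placebo groups". Within that scope, "Continuous endpoints measured only at Week 8 will be analyzed using linear regression (ANCOVA), with change from baseline to Week 8 as the response variable", with treatment group and "an appropriate baseline value as an additional covariate".

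The schedule of events (Protocol Table 2.1, SAP Appendix B) places CNS and the SF surveys at Week 0 and Week 8 with nothing at Week 4. That is the structure for which 8.6.1 prescribes ANCOVA.

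**The concern.** The trial collects a baseline for each of these scores, and the SAP already specifies a model that uses it, yet the exploratory p-values come from an unadjusted comparison of changes. Subtracting the baseline removes it with weight 1, whereas regression to the mean calls for weight r. When r is below 1 the change score therefore over-corrects, and part of any chance baseline difference carries into the comparison with reversed sign.

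Two features make this worth attention. Allocation is 3:1 in about 40 subjects, so the placebo arm has about 10. Randomization is stratified only on diary seizure frequency (SAP Section 3.4), so neither neurological score nor quality of life is balanced by design. At stake are the precision of a few exploratory comparisons and how their p-values read once the baseline table is known. No confirmatory result depends on them.

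**Working it through.** **Inputs.** About 40 subjects (SAP 3.1, 3.5) at 3:1 (SAP 3.3) give about 30 UX007 and 10 placebo; the first 3 were randomized 1:1, which shifts this little. Tests are one-sided at 5% (SAP 8.1). SF-10 is for ages 5 to 17 and SF-12 for 18 and over (SAP 5.8.6, 5.8.7). The correlation r between baseline and Week 8 is not in the documents, so it is an assumption shown over a range. Variances at the two visits are assumed equal (s²).

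**The plan's own figure.** No power or precision is stated for CNS, SF-10 or SF-12. The primary calculation (difference 50, SD 55, two-sample t-test, one-sided 0.05) claims about 80% power. With 10 vs 30 the noncentral t gives 78.8%, and the normal approximation 80.1%. The figure reproduces. Below, 78.8% serves only as a benchmark effect for the change-score t-test.

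**Chance imbalance.** The SD of the baseline mean difference is s·√(1/30 + 1/10) = 0.365s. The probability that it exceeds 0.5s in either direction is 17%. SF-10 and SF-12 divide the subjects by age, so each has fewer; an illustrative 5 vs 15 gives √(1/5 + 1/15) = 0.52.

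**What the change score leaves behind.** Given an observed baseline difference D, the expected difference in change is the treatment effect plus (r - 1)D, so the residual is -(1 - r)D. At D = 0.365s and r = 0.5 its size is 0.5 × 0.365 = 0.18s.

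**Precision.** Change-score variance is 2s²(1 - r). ANCOVA residual variance is s²(1 - r²). The ratio is (1 + r)/2. Estimating the slope multiplies this by 1 + 1/(N - 4), which is 37/36 = 1.028 at N = 40.

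| r | (1+r)/2 | ANCOVA SE / t-test SE, N = 40 | ANCOVA power where t-test has 78.8% | Size of residual at 0.365s imbalance |
|---|---|---|---|---|
| 0.5 | 0.75 | 0.88 | 87.3% | 0.18s |
| 0.7 | 0.85 | 0.94 | 83.4% | 0.11s |
| 0.8 | 0.90 | 0.96 | 81.5% | 0.07s |
| 0.9 | 0.95 | 0.99 | 79.6% | 0.04s |
| 0.95 | 0.975 | 1.00 | 78.7% | 0.02s |

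**Error rates by simulation** (10 vs 30, no treatment effect, 10,000 trials per case). Over all randomizations both methods reject about 5% of the time. Split by imbalance, with higher scores better:

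| r | t-test, UX007 baseline lower by more than 0.365s | t-test, UX007 baseline higher by more than 0.365s |
|---|---|---|
| 0.5 | 16% | 0.3% |
| 0.7 | 13% | 1.1% |
| 0.9 | 10% | 1.9% |

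ANCOVA stays at about 5% in every one of these cells.

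**Where ANCOVA stops helping.** Setting (1 + r)/2 × (N - 3)/(N - 4) = 1 gives a break-even of r = (N - 5)/(N - 3). That is 35/37 = 0.95 at N = 40, 7/9 = 0.78 at N = 12 and 3/5 = 0.60 at N = 8. At N = 8 and r = 0.7 the ratio is 0.85 × 1.25 = 1.06, so ANCOVA variance is about 6% higher.

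**The case against.** The best defence is that the tiering is deliberate. Table 5 gives model-based comparisons to primary and secondary endpoints and summaries to exploratory ones, SAP Section 4.3 presents the exploratory endpoints as supplemental, and Protocol Section 7.6 makes no multiplicity adjustment for them. A t-test on change is a legitimate simple test for that tier, unbiased over randomization and with its nominal error rate. This stands, and it keeps the point minor. It does not explain why data of the same structure are handled less efficiently when the method is already written.

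The second argument is that the gain depends on an unknown r. CNS includes height, weight, head circumference and reflexes (SAP 5.8.4), so a high correlation over 8 weeks is plausible. This also stands: near r = 0.9 there is little to gain.

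The third is sample size. Protocol Section 7.2 expects most subjects to be under 12, so few may qualify for SF-12, and in a very small subset ANCOVA can lose precision. This stands and limits the remedy.

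Three stronger readings are tempting and not supported:

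- A reader might infer that baseline imbalance is left uncorrected or that the tests are invalid. The change score does subtract baseline. It over-corrects, and only the error rate conditional on the imbalance is distorted.
- A reader might infer that adjustment is a free gain for every endpoint. The break-even values show otherwise for small subsets.
- A reader might extend the point to the CGI-I t-test. CGI-I is itself a rating of change with no baseline value, and CGI-S is a different scale given once at Week 0. The variance argument does not apply to it.

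**Conclusion.** The point holds as a low-severity improvement for CNS and SF-10, and conditionally for SF-12. With about 30 vs 10 subjects, unadjusted change-score t-tests give up about 25% of variance at r = 0.5, 15% at 0.7 and 10% at 0.8 in large-sample terms, and 5% or less at 0.9 and above, where the finite-sample cost largely cancels the gain. They also leave -(1 - r) times a baseline difference whose SD is 0.365 baseline SDs.

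This rests on an assumed r, equal variances at the two visits and near-complete CNS data (CNS is scored only when all domains are measured). The numbers for SF-10 and SF-12 are not given. A separate, purely documentary gap does not depend on r: the test for these p-values is stated only in output titles.

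**What to change.** In SAP Section 8.6.5, name the test: the 8.6.1 ANCOVA with treatment and the score's own baseline, for CNS and for each SF-10 summary score. Apply the same model to SF-12 when enough adults have data; otherwise invoke the rule at the end of 8.6.1 for insufficient observations, and state the minimum number in advance. Align the t-test rows of Table 6 and the Appendix A entries. Leave CGI-I as planned.

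The cost is a few lines of SAP and code and one residual degree of freedom, which matters only in very small subsets. No subjects are lost, because a change score already needs both values. The change should be made before unblinding; after that, report the ANCOVA as a labelled supplementary analysis.
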